6.2.1 Screening Evaluation

Screening evaluations will be collected weekly in clinic during months 1 and 2. Baseline mood, endocrine and sleep measures will also be collected during evaluation month 2.

Screening

All subjects will be screened via telephone to ensure they meet study criteria as defined in sections 4.1 (Inclusion Criteria) and 4.2 (Exclusion Criteria) above. Those that meet criteria will be scheduled for a screening interview with the Study Coordinator. Inclusion and exclusion criteria must be maintained throughout the study. Any deviation will be reported to the Study Coordinator and conveyed to the PI for evaluation and outcome determination.

During their initial screening visit in clinic, patients will complete a Menstrual Screening Form to assess mood and somatic symptoms, medication use and personal and family medical and psychological history. In addition we will obtain a urine toxicology screen and a pregnancy test.

Consenting Procedure

A written informed Screening Consent will be obtained from each subject at entry into the study to proceed with participation in the evaluation phase. After completion of the evaluation phase, qualified participants will sign a Study Consent before

proceeding with the treatment phase. Informed consent is obtained by the following process:

1. The subject will be asked to review the screening consent form.
2. The PI, Study Coordinator and/or one of their associates will meet with the subject to review the form, to confirm and to answer any questions the subject might have. The UCLA Office of Protection of Research Studies “Evaluation to Sign a Consent form for Research” will be administered to insure that all participants have understood the consent document, before they are asked to sign it.
3. Once the subject demonstrates understanding of the study and agrees to participate in the study, the consent will be signed in the presence of the Study Coordinator or a Research Associate and a witness.

6.2.2 Enrollment, Baseline, and/or Randomization

Baseline Assessments

In accordance with the Schedule of Evaluations (section 6.1 above), baseline measures will be collected in Evaluation Month 2 as follows:

- Hamilton: The Hamilton Rating Scale for Depression (HRSD)⁵⁶ (as a validated objective, interview-based assessment of depression). Atypical depression symptoms as part of the Structured Interview Guide for the Hamilton Depression Rating Scale, Seasonal Affective Disorders version (SIGH-SAD)⁶⁰ (as atypical symptoms in particular respond to light treatment⁶¹) Mania⁶² ratings (to document any clinical induction of manic symptoms by the wake or light interventions) – once weekly for 8 weeks,
- Beck Depression Inventory (BDI)⁵⁷ (as a validated subjective assessment of depression) – once weekly for 8 weeks,
- Beck Anxiety Inventory (BAI)⁵⁸ (as many women with PMDD report anxiety symptoms)⁶³ – once weekly for 8 weeks,
- The Psychological General Well-Being Index (PGWI)⁶⁴ – once weekly for 8 weeks,
- Daily mood self-ratings (DMR)⁵⁴ that include core PMDD symptoms of anxiety and irritability – daily for 8 weeks,
- Expectation form measuring patient expectation for change with the interventions (100 mm line from “much worse” to “much better”) – completed once,
- Horne-Östberg scales to assess morningness and eveningness⁶⁵ – completed once,
- Seasonal Pattern Assessment Questionnaire (SPAQ)⁶⁶ – completed once,
- Pittsburgh Sleep Quality Index (PSQI)⁶⁷ to assess subjective sleep quality – once in month 1 and month 2,
- Visual analogue scale⁶⁸ to assess subjective sleep quality – once in month 1 and month 2,

- Structured Clinical Interview for DSM-IV (SCID)^{51, 52} – completed once to establish diagnosis in evaluation week 8,
- Ovulation testing performed for 7 days starting on menstrual cycle day 10 in month 2 to determine luteinizing hormone surge (LHS). Participants will contact Study Coordinator with their time of first menses (cycle day 1) to determine cycle day 10 and schedule appointment for collecting study forms and equipment,
- Actigraphy will be collected for 10 days starting the day of LHS to monitor baseline sleep, light and activity measures at home,
- Urine collection for 30 hrs performed between days 8-9 after LHS.

Enrollment

Enrollment in the evaluation phase of the study occurs at the time of first screening visit when patients sign a Screening Consent form.

Enrollment in the treatment phase occurs during a clinic visit scheduled between cycle days 1 and 10 of the menstrual cycle immediately following successful completion of the evaluation phase (Month 3), provided they are qualified to participate and they sign a Study Consent form. During this visit, they will also be assigned an individual participant identifier (Master Code Number) and be randomized to the first of two treatment conditions. Enrollment ascertainment for the treatment phase and randomization occur at the same time.

Randomization

All subjects for this study will be enrolled in the evaluation phase of the study at the time of the first screening visit when patients sign a Screening Consent form. Enrollment in the treatment phase occurs during a clinic visit scheduled between cycle days 1 and 10 of the menstrual cycle immediately following successful completion of the evaluation phase (Month 3), provided the subject is qualified to participate. During this visit, we will randomize subjects to the first of two treatment conditions. Starting on the day of ovulation, subjects will be randomized to either 1) one night of Late Wake Therapy (LWT: sleep 21:00-01:00 h, followed by wakefulness) plus 7 days of AM Bright White Light (BWL: light-emitting diode-LED administered for 60 minutes, starting within 30 minutes of habitual wake time) or 2) Early Wake Therapy (EWT: wakefulness until 03:00 h, then sleep 03:00-07:00 h) plus 7 nights of PM BWL (administered 90 minutes before habitual sleep onset, for 60 minutes). The problem of randomization imbalance, observed particularly when independent groups (such as group 1 receiving only treatment A and group 2 receiving only treatment B) are used, will be addressed by two processes. First, this study uses a cross-over design and subjects will be assigned to the other treatment in the luteal phase of their next menstrual cycle after a one-month washout period. Second, subjects will be randomized to study treatment group in a 1:1 ratio with variably-sized block design. This randomization will be done using SAS programs that we have used for many of our clinical trial studies. The block sizes are known only to the study statistician. The randomization table will be prepared prior to the initiation of the study.

Note, only subjects who meet all of the inclusion criteria and none of the exclusion criteria after successful completion of the evaluation phase are eligible for randomization into the treatment phase.

In addition to violations of inclusion and exclusion criteria, we also will document in the patient's chart reasons for randomization failure, any protocol deviations and reasons why subjects were lost to follow-up, voluntarily withdrew and/or were terminated from the study.

Participants will be assigned for study between cycle days 1 and 10 of Month 3 and will begin the wake therapy component of Treatment 1 at time of ovulation, which may occur between cycle days 10 and 17. Treatment 2 will occur in Month 5, approximately two months after randomization. If a patient does not ovulate, treatment will be delayed until the following menstrual cycle, thereby increasing the time between randomization and each treatment condition by approximately 1 month, the maximum allowable period.

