6. STUDY PROCEDURES

6.1 Schedule of Evaluations

	Screening	Evaluation Period								Treatment 1 Month 3			WASHOUT Month 4	Treatment 2 Month 5			Follow-Up: Final Visit				
		Month 1				Month 2				Menstrual Cycle Day 10	Ovulation* (Luteinizing Hormone surge – LHS)	LHS → LHS+2 days*		LHS → LHS+10 days	LHS+8 → LHS+9 days	Menstrual Cycle Day 10		Ovulation* (Luteinizing Hormone surge – LHS)	LHS → LHS+2 days*	LHS → LHS+10 days	LHS+8 → LHS+9 days
		Eval WK1	Eval WK2	Eval WK3	Eval WK4	Eval WK5	Eval WK6	Eval WK7	Eval WK8												
Screening Consent	X																				
Urine Toxicology Screen	X														X						
Menstrual Assessment Questionnaire	X																				
Ovulation Testing (7 days)									X												
Hamilton		X	X	X	X	X	X	X	X						X					X	X
BDI		X	X	X	X	X	X	X	X						X					X	X
BAI		X	X	X	X	X	X	X	X						X					X	X
PGWI		X	X	X	X	X	X	X	X						X					X	X
Daily Mood Ratings		X	X	X	X	X	X	X	X						X					X	X
SCID									X												
Study Consent										X											
Randomization										X											
SPAQ										X											
Expectation Form										X											
Horne and Ostberg										X											
PSQI					X				X												X
Visual Analogue Scale Sleep Quality Rating				X				X													X
Actigraphy (10 days)									X					X					X		
Urine Collection (30 hrs)																					X
Side-Effects Checklist																					X
Global Assessment of Treatment Effectiveness																					X

* Evaluations (Hamilton and Becks) over the phone.

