6.2.3 Blinding

The principal investigator and clinical rater will remain blind to treatment condition until completion or discontinuation of participant from study. As patients will be coded, one statistician and technician and supervisor running assays also will be blind to patient name and treatment condition. Members of the Data Safety Monitoring Committee will review records in which patient names are coded, unless the code needs to be broken in the event of an adverse outcome. All other lab personnel will not be blind to treatment as the study coordinator and research associate prepare patient equipment and instruct patients on proper completion of the treatment protocol, the data manager and quality assurance officer enter all data into the database (including treatment condition). Due to the nature of the treatment (sleep, light intervention), patients will not be blind to condition.

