9.5.2 Secondary Outcomes

- Effects of expectation, morningness/eveningness and seasonality on primary outcome measures:
Prior to entering the study, subjects will complete expectation forms measuring their expectation for change with the interventions (100 mm line from "much worse" to "much better") as well as Horne-Östberg scales to assess morningness and eveningness, as these variables may mediate or moderate primary outcome measures. To determine whether seasonality affects outcome, subjects will complete the Seasonal Pattern Assessment Questionnaire (SPAQ).
- Treatment-related changes from baseline (month 2) and 1-2 days post intervention (months 3,5) in reproductive hormones:
We will obtain overnight urinary samples for estradiol, progesterone, gonadotropins and prolactin (obtained at the same time of 6-SMT overnight collections in baseline and intervention months).
- Subjective visual analog scale-based global assessment of treatment effectiveness:

Following both treatment interventions, subjects will complete a visual analog scale-based global assessment of treatment effectiveness.

- Subjective assessment of side effects to treatment: collected 1-2 days post intervention (months 3,5)

Following each treatment interventions, subjects will complete an assessment of side effects using the Side Effects Checklist.

As delineated in our Data and Safety Monitoring Plan, the Independent Monitoring Committee will meet on an annual basis to review outcome data. The committee will be masked to a participant's intervention group assignment.

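### As described, expectation is rated once for both treatments together, so differential expectation, a plausible rival explanation in this unblinded crossover, is not measured

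*Combined protocol and SAP*

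**What the plan says.** Section 6.2.2 lists among the baseline measures an "Expectation form measuring patient expectation for change with the interventions", described as a 100 mm line anchored at much worse and much better and filled in on one occasion. Section 9.5.2 gives the timing differently: "Prior to entering the study, subjects will complete expectation forms measuring their expectation for change with the interventions". In the schedule (section 6.1) the "Expectation Form" row carries a single mark, apparently in the Month 3 column with Study Consent and Randomization; the table layout is damaged, so that position is approximate. Neither the treatment-visit list (section 6.2.4) nor the Month 5 steps in Appendix I repeat the form. The Side Effects Checklist, by contrast, is explicitly tied to each treatment in section 9.5.2.

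On blinding, section 6.2.3 says: "Due to the nature of the treatment (sleep, light intervention), patients will not be blind to condition". It also says: "The principal investigator and clinical rater will remain blind to treatment condition".

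Section 1.2 makes the effect of expectation on mood, melatonin and sleep a secondary objective, and section 9.5.2 treats expectation as a possible mediator or moderator. Section 9.6 says only that the forms will be looked at against the size of the mood change. It names no expectation term or treatment-by-expectation interaction in the random regression model.

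**The concern.** The trial compares two active treatments within the same woman, and she knows which one she is receiving. BDI, BAI, PGWI and DMR are her own ratings and stand among the primary mood outcomes (section 9.5.1). The HRSD rater is blind, but the interview still rests on what she reports. The study hypothesis favours LWT+AM BWL, and unmasked staff give the instructions (section 5.2). The documents do not show what patients are told about the relative merit of the two treatments.

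The expectation that matters for the treatment contrast is therefore differential: more hoped for from one treatment than from the other. A single rating of both together contains no information on this. If the mood contrast is positive, a reader will ask whether expectation could account for it, and the trial could not answer from its own data. A rating not taken before allocation cannot be recovered later.

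**Working it through.** The plan states no figure on this point, so there is none to reproduce. The check is algebraic, followed by a range under stated assumptions.

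**Inputs from the documents (section 9.2).** Planned HRSD difference 3.15, SD 9, N = 40, two-tailed tests. I take 9 as the SD of the within-woman difference; the text does not say so.

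**Assumed inputs.** Slope *s*, in HRSD points of improvement per mm of expectation: 0.05 to 0.2. Mean expectation gap *G*, LWT+AM BWL minus EWT+PM BWL: 5 to 30 mm. The documents give neither.

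**Step 1: cancellation.** For woman *i*, let d_i be her improvement on LWT+AM BWL minus her improvement on EWT+PM BWL. Then

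d_i = treatment effect ± period effect + s × (E_i,AM − E_i,PM) + error.

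With one joint score, E_i,AM and E_i,PM are both recorded as E_i, and s × (E_i − E_i) = 0. The main effect of the recorded score drops out, while a real gap stays in d_i. The bias in the mean contrast is s × G.

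**Step 2: size of s × G**, in HRSD points and as a share of 3.15.

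| Gap | s = 0.05 | s = 0.1 | s = 0.2 |
|---|---|---|---|
| 5 mm | 0.25 (8%) | 0.5 (16%) | 1.0 (32%) |
| 10 mm | 0.5 (16%) | 1.0 (32%) | 2.0 (63%) |
| 20 mm | 1.0 (32%) | 2.0 (63%) | 4.0 (127%) |
| 30 mm | 1.5 (48%) | 3.0 (95%) | 6.0 (190%) |

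The gap that would by itself produce the whole 3.15 is 3.15/s: 63 mm, 31.5 mm or 15.75 mm. With no true effect, a two-sided paired t-test (n = 40, SD 9) rejects in 5.3% of trials at a bias of 0.25, 28% at 2.0 and 98% at 6.0.

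**Step 3: simulation.** 2×2 crossover, 20 women per sequence, complete pairs, no true effect, gap SD 10 mm between women, 2,000 runs per setting. Negative means lower HRSD on LWT+AM BWL.

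| Gap, slope | No expectation term (rejects) | Joint score added | One score per treatment (rejects) |
|---|---|---|---|
| 10 mm, 0.1 | −1.03 (11%) | −1.03 | −0.03 (6%) |
| 20 mm, 0.1 | −1.98 (27%) | −1.98 | 0.19 (5%) |
| 15 mm, 0.2 | −3.01 (54%) | −3.01 | −0.01 (4%) |

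Adding the joint score changed the estimate by less than 1e-12 in every run. The target in the last column is 0; the 0.19 is simulation error.

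**Step 4: what the joint score can still do.** A treatment-by-expectation interaction is estimable, as the correlation between E_i and d_i. For r = 0.43 and 40 pairs, atanh(0.43) × √37 = 0.460 × 6.08 = 2.80, and Φ(2.80 − 1.96) is about 0.80. Only a correlation near 0.43 or larger would be found with 80% power.

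**Step 5: price of adjustment.** The treatment effect at zero expectation difference is the intercept of d_i on that difference. Its standard error is roughly (9/√40) × √(1 + (mean gap/SD of gap)²). With a mean gap of 20 mm and SD 10 mm this is 1.42 × √5 = 3.18, against 1.42 unadjusted.

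**The case against.** The form is not in the documents. Section 9.5.2 speaks of forms and interventions in the plural, and being filled in on one occasion fixes the number of occasions, not the number of lines. A line per treatment is possible. One joint line is the more natural reading of section 6.2.2, but the point depends on it.

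The plan also never promises to adjust the treatment contrast for expectation. Sections 1.2, 9.5.2 and 9.6 ask whether expectation relates to outcome, and one pre-treatment score can show whether women who expect more improve more, or whether the treatment difference varies with expectation. A reader might infer that the expectation data are useless or can explain nothing; that goes too far. What stands is that the mediation part of the aim is out of reach for the average contrast.

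The design limits the risk. The rater and principal investigator are blind, both arms are active with the same light device and seven days of light, and urinary 6-SMT, also a primary outcome, is not self-rated. Nothing in the documents indicates the size or sign of any expectation gap. A blind rater does not, however, remove patient expectation from self-rated scales.

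Finally, exact cancellation needs complete pairs. With dropout after the first treatment the mixed model uses some between-woman information, so the joint score could move the estimate slightly, still without capturing differential expectation.

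**Conclusion.** The point holds in limited form. If the form is one joint line, it cannot adjust the average within-woman contrast on complete pairs or test mediation of it, and differential expectation goes unmeasured in an unblinded comparison with self-rated primary outcomes. It is a cheap improvement that serves a stated secondary objective, not a flaw that invalidates the primary analysis.

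The documents do not support two stronger readings. One is that expectation would account for some particular share of the planned difference: the assumed inputs span 8% to 190% of 3.15, so no single share is informative, and the figures are for HRSD, the blind-rated scale, only because the plan supplies a usable planning difference for it. The other is that the form in effect sets the expectation gap to zero: it does not estimate the gap at all. Nor is there evidence that the contrast is in fact biased.

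**What to change.** - State what the form contains. If it already has a line per treatment, say so; only the timing and the analysis then need attention.
- Otherwise, collect one 100 mm line for each treatment at the existing Month 3 pre-intervention visit, before randomization or disclosure of sequence.
- Reconcile the timing, which now reads as Month 2 baseline (section 6.2.2), before study entry (section 9.5.2) and apparently the randomization visit (section 6.1), and state that the form precedes disclosure.
- Pre-specify a sensitivity analysis of the mood contrast: regress the within-woman outcome difference on the pre-allocation within-woman expectation difference, uncentred, with period in the model (sequence coded ±½). The intercept is then the treatment effect at equal expectation. Mean-centring the covariate would return essentially the unadjusted contrast.
- Treat any repeat in Month 5 as descriptive only. It follows the response to the first treatment, so adjusting for it could remove part of a real effect.

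The cost is one extra line per woman at a visit already scheduled. The sensitivity estimate depends on the assumed linear relation, will have wider error bars, and captures only expectation held before allocation. It should be read beside the primary analysis, not in place of it.

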6.2.3 Blinding

The principal investigator and clinical rater will remain blind to treatment condition until completion or discontinuation of participant from study. As patients will be coded, one statistician and technician and supervisor running assays also will be blind to patient name and treatment condition. Members of the Data Safety Monitoring Committee will review records in which patient names are coded, unless the code needs to be broken in the event of an adverse outcome. All other lab personnel will not be blind to treatment as the study coordinator and research associate prepare patient equipment and instruct patients on proper completion of the treatment protocol, the data manager and quality assurance officer enter all data into the database (including treatment condition). Due to the nature of the treatment (sleep, light intervention), patients will not be blind to condition.

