Using a randomized cross-over design, in the luteal phase of their menstrual cycles, PMDD women will receive either 1) one night of LWT (sleep 21:00-01:00 h, followed by wakefulness) plus 7 days of AM BWL (light-emitting diode-LED administered for 60 minutes, starting within 30 minutes of habitual wake time) or 2) EWT (wakefulness until 03:00 h, then sleep 03:00-07:00 h) plus 7 nights of PM BWL (administered 90 minutes before habitual sleep onset, for 60 minutes). Following this first intervention, patients will undergo one washout month with no intervention. The second intervention will be completed in the luteal phase of the following month and will be the treatment opposite the one previously performed. Total study duration, including evaluations and washout, will be 5 months (see Figure 1, Section 3, for detailed study flow diagram).

Sample Size and Population

In order to achieve the targeted enrollment goal of 40 completed subjects allowing for a 20% drop-out rate, 48 PMDD women ages 18-45 will be recruited to participate in the study.

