6.2.6 Follow-up/Final Evaluation

During final visit, subjects will again perform the Hamilton, BDI, BAI and PGWI ratings (once). They will also complete the Global Assessment of Treatment Effectiveness form. Final evaluation of inclusion/exclusion criteria will be performed at this time.

After completion of the study (final visit), participants will be followed up for 1 month to monitor relapse. The Clinical Rater will telephone the patient at home during the luteal phase, around the same time in the patient's cycle as the post treatment 2 ratings were collected, to collect follow-up mood ratings (Hamilton, BDI, BAI and PGWI).

None of the subjects will be excluded from analysis, and their data will be analyzed according to the randomization scheme. Different hypotheses are included for different phases of the study. All subjects will be included in any baseline analyses regardless of their final study status. In addition to the baseline data, at least one other data point is needed in order to provide a valid estimation of a parameter for change throughout the study. The Random Regression Model was selected due to the flexibility of this method that includes all subjects with any valid data point in the analyses, as opposed to a method that is designed to examine just

the completers, such as a Repeated Measures Analysis of Variance. All subjects will be included in the analyses and we will not focus only on subjects who complete the study. Secondary analyses will be performed on data from completers. Our methods for data analyses include all subjects with any valid data points in the analyses (see Section 9.6. General Approach to Data Handling and Statistical Analyses).

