9.6 Data Analyses

Analysis will be performed on data from subjects qualified for participation in accordance to DSM-IV criteria for PMDD (see section 4.3 for criteria and symptoms) as confirmed prospectively by Daily Mood Ratings (DMR).

Mood and Other Ratings: In study month 3 (first treatment), month 4 (washout), month 5 (second treatment) and month 6 (follow-up), we will examine objective (HRSD, atypical, mania – to evaluate symptom severity) and subjective (Beck– to evaluate symptom severity, visual analogue scale-*DMR*) mood (including irritability and anxiety) and physical symptom ratings as a function of diagnosis and time of wake/light interventions.

6-SMT data processing and circadian analyses: From the 6-SMT concentration, urine volume, and the collection times, the 6-SMT excretion rate (ng/h) is computed for each collection interval (the interval between one voiding and the next). Circadian parameters then are computed from analyses of the full time series of 5-min intervals representing each overnight collection. The best-fitting 24-hour cosine curve (for an assumed period of 24 h) is estimated with a least-squares technique to yield the acrophase time (peak), amplitude (1/2 height) and mesor (mean excretion rate (ng/h)) of the fitted curve. To further describe changes in circadian phase and waveform, we use the actual ng/h curve to estimate the circadian timing of nocturnal 6-SMT onsets and offsets algebraically from upward (onset) and downward (offset) crossings of the cosine mesor.

Reproductive Hormones: Levels will be correlated with circadian measures and mood ratings to determine reproductive hormonal influences on circadian physiology and mood.

Daily Sleep Logs will be analyzed for rhythm stability (consistency of standard deviations of sleep onset and offset times from night to night), before vs. after the interventions.

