 - e. Day after LHS (LHS+1) – commence first light treatment (for 7 days)
 - f. LHS+8 → LHS+9 – commence urine collection (30 hrs)
 - g. LHS+11 – equipment, samples and forms are returned to lab
5. Washout (Month 4)
- a. Perform clinical ratings only
6. Treatment 2 (Month 5)
- a. Record CD1 (patient will call Study Coordinator with date and to schedule pre-intervention in-office visit)
 - b. Pre-Intervention Visit – to be completed between cycle days 1 and 10:
 - i. Provide ovulation test kit
 - ii. Provide urine collection kit
 - iii. Provide Actiwatch Spectrum
 - c. Menstrual Cycle Day 10 – commence testing for LHS (7 days of testing)
 - d. Ovulation Day (LHS) – commence actigraphy recording (for 10 days)
 - commence Wake Therapy (1 night)
 - e. LHS+1 – commence first light treatment (for 7 days)
 - f. LHS+8 → LHS+9 – commence urine collection (30 hrs)
 - g. LHS+11 – equipment, samples and forms are returned to lab
7. Final Visit (can be performed at time of item 6.g. above)
- a. Review side effects to treatment and subjective global assessment of treatment effectiveness.
8. Follow-up (luteal phase in the month following Treatment 2)
- a. Perform clinical ratings per telephone.

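### The clinical rater's blind may end at the final visit, before the Month 6 relapse HRSD that the same rater scores and the plan examines by intervention

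*Combined protocol and SAP*

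**What the plan says.** Section 6.2.3 (Blinding) sets the end of the blind woman by woman: "The principal investigator and clinical rater will remain blind to treatment condition until completion or discontinuation of participant from study". The same section says that participants, the study coordinator, the research associate, the data manager and the quality assurance officer are not blind.

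Section 6.2.6 (Follow-up/Final Evaluation) fixes what completion means and what comes after it: "After completion of the study (final visit), participants will be followed up for 1 month to monitor relapse". It then names who does the follow-up: "The Clinical Rater will telephone the patient at home during the luteal phase". The ratings taken on that call are the Hamilton, BDI, BAI and PGWI. The legend to Figure 1 in Section 3 also lists an HRSD after the second intervention to monitor relapse.

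Appendix I, item 7, lets the final visit coincide with item 6.g, the return of equipment and samples at LHS+11 of Month 5. Item 8 places the follow-up in the luteal phase of the next month. The Précis agrees with completion in Month 5: "Total study duration, including evaluations and washout, will be 5 months".

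Section 9.6 (Data Analyses) brings the follow-up month into the data to be looked at: "In study month 3 (first treatment), month 4 (washout), month 5 (second treatment) and month 6 (follow-up), we will examine objective" and subjective ratings, as a function of the time of the wake and light interventions.

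**The concern.** Women know which regimen they are receiving, and the BDI, BAI, PGWI and daily ratings are their own reports. The HRSD, with its atypical and mania items, is the interviewer-scored measure, and a blinded rater is the only masking that the mood assessment has. Sections 2.2 and 9.1 explain why the two regimens are contrasted, and the Précis and Section 9.1 state in advance that late wake therapy with morning light is expected to do better.

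If the code may be opened at the final visit, the Month 6 Hamilton can be scored by a rater who knows the order of treatments. By then every completer has had both regimens, so the code reveals which one came last. A comparison of relapse or durability after the second treatment depends on exactly that. It is also a comparison between women, about 20 per sequence if 40 completers divide evenly under the 1:1 allocation (40 / 2 = 20), and so it lacks the within-woman control of the main crossover contrast.

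**Working it through.** The point rests on the order of events, so the check sets the sections side by side. The only arithmetic is for scale.

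**Order of events for a completer**

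| Step | Timing | Source | Blind required? |
|---|---|---|---|
| Month 3 ratings | LHS, LHS+1, LHS+2, LHS+8 to +9 | 6.2.4 | Yes |
| Washout rating | Month 4, luteal phase | 6.2.5 | Yes |
| Month 5 ratings | LHS, LHS+1, LHS+2, LHS+8 to +9 | 6.2.4 | Yes |
| Final visit (completion) | LHS+11 of Month 5 at the earliest | 6.2.6; Appendix I, items 6.g and 7 | Yes, up to completion |
| Relapse call by the clinical rater | Luteal phase of Month 6 | 6.2.6; Appendix I, item 8 | No |

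**Gap between completion and the call.** Section 6.2.6 times the call to about the same point in the cycle as the ratings after the second treatment, that is LHS+8 to +9. Section 4.1 requires cycles of 26 to 32 days. Assume that one LH surge follows the last by one cycle length, and that the final visit is at LHS+11:

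- shortest gap: 26 + 8 − 11 = 23 days
- longest gap: 32 + 9 − 11 = 30 days

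So for roughly 23 to 30 days before the call, nothing in 6.2.3 requires the rater to remain blind.

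**Share of HRSD ratings exposed.** Planned Hamilton ratings per woman after randomization:

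- Month 3: 4
- Month 4: 1
- Month 5: 4
- Final visit: 1
- Month 6: 1
- Total: 4 + 1 + 4 + 1 + 1 = 11

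One of these follows completion: 1 / 11 = 9%. With 40 completers that is 40 × 1 = 40 interviewer ratings out of 40 × 11 = 440.

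**Does the exposed rating reach a defined outcome?** Section 9.5.1 defines the primary mood outcome as change from Month 2 to the post-intervention ratings in Months 3 and 5. Neither 9.5.1 nor 9.5.2 lists Month 6 or relapse. Section 9.6 does name Month 6 among the months to be examined. It also says that the random regression model uses every subject with any valid data point, without saying whether Month 6 is a time point in that model. The rating is therefore planned for examination, and its place in the model is left open.

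**Does any other text extend the blind?** Section 10.1 calls the rater blind and gives her all the mood forms, but sets no end date for the blind. Section 4.1 speaks of a study of up to 6 months, but does not define completion. No section carries the blind to the last follow-up rating or to database lock.

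**The case against.** The best case for the plan has three parts.

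First, 6.2.3 permits unblinding but does not order it, and no section tells anyone to give the rater the code. The description of the rater as blind in 10.1, the six-month wording in 4.1, and the treatment of Month 6 as a study month in 9.6 leave some room to read completion as including follow-up. This stands as a limit on strength: the rating may be unblinded, not will be. It does not close the gap, because 6.2.6 identifies completion with the final visit and puts the call after it.

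Second, no listed outcome uses Month 6. This stands, and it keeps the point modest.

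Third, only one interviewer rating per woman is exposed, and the code reveals order alone. This also stands. Order is nonetheless what a relapse comparison turns on.

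A reader might infer more than the documents support:

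- **That the primary HRSD result is compromised.** Completers' Month 3 and Month 5 ratings all precede completion.
- **That the final-visit Hamilton is exposed too.** The visit is itself the completing event, so a rating made at it falls within the blind.
- **That eight women (48 − 40) would have unblinded exit ratings.** No mood rating is scheduled at or after early discontinuation. The exit interview in 10.3.3 concerns satisfaction and problems with the protocol. The 48 are women recruited, and the documents do not say how many of the eight would leave before randomization, when there is no allocation to reveal.
- **That opened codes would let staff predict later allocations.** Section 6.2.2 specifies variable block sizes known only to the statistician, and the evaluation ratings that decide eligibility precede randomization.
- **That adverse-event attribution is unblinded for six months.** The six months in 7.5 concern following events. Under 7.3, events are recorded as they occur and reported to the principal investigator for review. Only late-onset events or revised attributions could be exposed.

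**Conclusion.** The concern holds in a limited form. As written, the plan allows the clinical rater and principal investigator to learn a woman's treatment sequence before the Month 6 relapse HRSD, which the rater scores and the plan examines by intervention. The reach is one interviewer rating per completer, up to 40. The primary mood ratings of completers are unaffected, and ratings after early discontinuation are affected only if someone takes them.

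The conclusion assumes that completion means the final visit, as 6.2.6 says. If the sponsor meant completion to include the follow-up call, the sections still need to be made consistent. The documents give no basis for estimating how far an unblinded rater would shift the scores. The change is worth making because the exposure is avoidable and cannot be repaired once codes are opened.

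**What to change.** Amend Section 6.2.3 so that the clinical rater and principal investigator stay blind to a woman's treatment sequence at least until her last mood rating. That should include the Month 6 call and any rating taken after discontinuation. Database lock is the preferable end point.

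State that any earlier code break for safety is documented, with its date, and that the woman's later HRSD ratings are flagged as unblinded in the data. The code-break clause now in 6.2.3 concerns the monitoring committee's review of coded records, so a route for the investigator has to be written. Section 9.6 should also say whether Month 6 enters the random regression model, and how flagged ratings are treated.

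The cost is small: a short wording change, a defined code-break route and one data flag. No visits or staff are added, because the unblinded coordinator and research associate already handle equipment and treatment instructions (5.2, 6.2.3).
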